10.8 Handling of Missing Data

For all primary and secondary statistical analyses described above, multiple imputation will be used for all missing values except those due to participant death. To ensure that the missing at random assumption for multiple imputation is valid, we will compare baseline pain or depression scores and other patient characteristics in those lost to follow up to participants retained on their randomization assignment. We will also do sensitivity analyses where we compare results obtained with multiple imputation to those obtained without imputation. Missing values due to death will not be imputed and will therefore not be included in the analyses. For exploratory repeated measures analyses, missing data are easily handled as long as the missing at random assumption is valid. However, the missing at random assumption cannot be tested. Accordingly, for exploratory analyses using repeated measures mixed models, we will also conduct a sensitivity analysis where missing values are imputed using multiple imputation. The results with and without multiple imputation will be compared. More complete details of the handling of missing values under different circumstances will be described in the SAP.

10.9 Multiplicity

With the primary and various secondary endpoints that have been outlined, there is a multiplicity of analyses to be performed, which leads to an increased probability that at least one of the comparisons could be "significant" by chance. Adjusting for the effects of the repeated significance testing for the

multiplicity of secondary endpoints would require that very small significance levels be used for every comparison. Therefore, rather than adjusting for multiple comparisons, we will be conservative in the interpretation of the analyses, considering the degree of significance, and looking for consistency across endpoints. The nominal (unadjusted) p-value for each comparison will be reported to aid in the overall interpretation. We have also prespecified the primary and secondary outcome variables to avoid over-interpretation of strictly exploratory comparisons.

11. DATA MANAGEMENT

11.1 Data Entry and Record Keeping

ADOPT PGx data sources include: data collected from participant surveys, genetic testing results, data from the EHR, and CMS billing records. Data will be entered into a REDCap database maintained by the CC by trained and qualified personnel at each clinical site for baseline and follow-up assessments and by the UF call center for follow-up assessments. Site staff will receive training on the use of the REDCap database. After staff are trained, they will receive a unique user identification and password to access data entry forms for their site. Access codes should not be shared and are non-transferable.

Laboratories will transfer genetic testing results to the IGNITE PTN CC and follow standard site-specific return of results procedures for providers. The genotype and result (i.e. metabolizer phenotype) for each participant will then be imported to the participant's study database record from laboratory produced output files. The accuracy of the import of laboratory results will be verified by comparing the results recorded in the study database to an external record of the result for a subset of the study participants. See MOP for details.

Sites will extract the relevant data from their EHR (see Section 7.7) and transfer of those data to the IGNITE PTN CC following procedures that will be specified in the MOP. Briefly, sites will be given a list of trial-specific information to extract for their ADOPT PGx participants, a common format that data should be converted to, and procedures for secure file transfer to the CC.

11.2 Data Element Definitions

Clinically significant pain reduction: Whether or not the pain reduction score is ≤ 0.7 . If the pain reduction score is ≤ 0.7 , clinically significant pain reduction is achieved, if pain reduction scores is > 0.7 , clinically significant pain reduction is not achieved.

Depression symptom control: The change in the PROMIS Emotional Distress - Depression 8b or PROIMIS pediatric Depression 8a survey depression score from baseline to time t.

Depression remission: A. Whether or not the summed raw PROMIS emotional distress depression 8b survey responses are ≤ 16 , which is equivalent to the participant responding “rarely” or “never” to most or all of the PROMIS emotional distress - depression 8b survey questions. B. Whether or not the PHQ-8 scores are ≤ 4 , which is equivalent to depression severity being none-mild.

Depression (PHQ-8) score: The sum of the responses to the PHQ-8 survey, range from 0 to 24.

Depression (T) score: The T-score converted summed responses to the PROMIS emotional distress depression 8b survey. The T-score conversion is centered around 50 with standard deviation of 10.

Depression severity: The depression score converted to depression severity (none, mild, moderate, severe) based on the scoring guide for the PROMIS emotional distress depression 8b survey.

Medication adherence: The scored responses to the Voils Medication Adherence survey.

Medication concordance: Whether or not the medication the participant is prescribed after the intervention is concordant with the participants CYP2D6 and, for the depression trial, CYP2C19 phenotype.

Medication side effects severity burden: (Depression only) The sum of the scored severity (none = 0, mild = 1, moderate = 2, severe = 3) for common SSRI side effects.

Opioid misuse score: The T-score converted summed responses to the PROMIS prescription medication misuse 7a survey. The T-score conversion is centered around 50 with standard deviation of 10.

Opioid persistence: Defined as ≥ 1 opioid prescription refill between 90 days and 180 days after the surgical procedure.

Opioid usage: The average daily morphine equivalents in mg (MED) in past 7 days. MEDs will be calculated using data from the opioid usage survey.

Overall well-being: Defined as the T-score converted summed responses to the PROMIS 43/PROMIS 37 pediatrics survey. The T-score conversion is centered around 50 with standard deviation of 10.

Pain control: The difference in pain intensity score at follow-up time t and the baseline pain intensity score.

Pain intensity score: The mean of average pain in the last 7 days, current pain, and worst pain in the last 7 days. Average pain, current pain, and worst pain will be collected using the 3-question PROMIS pain intensity scale.

Pain reduction score: The ratio of the pain intensity score (derived from the PROMIS pain intensity survey) at follow-up time t to the baseline pain intensity score.

Silverman integrative analgesic assessment (SIA) score: This is an integrated measure of pain and opioid usage, calculated as follows: pain and opioid usage are ranked, the ranks are converted to percentiles and linearly transformed such that the scores are centered at 0 and range -100 to 100. The pain scores and opioid usage transformed percentiles are summed to generate the SIA score that ranges -200 to 200. Negative values indicate low pain with minimal opioid usage, while positive values indicate higher pain with higher opioid usage. See Appendix A for additional details and supporting rationale.

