PROMIS pediatrics 37 – Pediatric study participants (ages 8-17) will complete a 37-question survey assessing pediatric well-being and sub domains: pain interference, physical function, sleep disturbance, social role and activities functioning, fatigue, anxiety, and depression. This survey will be administered to pediatric participants at baseline, 1-month, 3-months, and 6-months post-surgery (acute pain), or baseline, 1 month, 3 months, and 6 months post return of results (depression).

Health care utilization – Survey of the number of significant cost driver health care encounters (e.g. hospitalizations, clinic visits, etc.). This survey will be administered to participants at 10-day, 1-month, 3-months, and 6-months post-surgery (acute pain), or baseline, 1-month, 3-months, and 6-months post return of results (chronic pain, depression).

Medications - Participant medications will be collected using patient surveys at baseline and the primary endpoint time points: 10-days for Acute Pain and 3-months for Depression and Chronic pain.

Productivity loss – Survey of loss of work the time and pay lost due to the participant's depression or pain. This survey will be administered to participants at 1-month, 3-months, and 6-months post-surgery (acute pain), or 1-month, 3-months, and 6-months post return of results (chronic pain, depression).

Acute Pain:

PROMIS Numeric Rating Scale - Pain Intensity - An 11-point numeric scale ranging from 0 (no pain) to 10 (worst possible pain) for average pain. This survey will be administered to all participants at baseline, 10 days, 1-month, 3-months, and 6-months post-surgery.

PROMIS pain intensity scale – A participant completed 3-question survey of average pain over the last 7 days, worst pain over the last 7 days, and current pain. Each question is on a 1-5 integer scale, the higher the value, the more intense the pain. This survey will be administered to all participants at baseline, 10 days, 1-month, 3-months, and 6-months post-surgery.

Opioid consumption questionnaire – A participant completed survey of pain prescription medication consumption, including the type of opioid pain medication, number of pills dispensed, if a refill has been obtained, and the number of pills left for each opioid pain medication selected. This survey will be administered to all participants at 10 days and 1-month post-surgery.

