7.9 Data Collection from CMS and State Medicaid Agencies

Medicare and Medicaid claims data from CMS and state Medicaid agencies will be used to assess health care utilization, costs, and medications among participants covered by either Medicare or Medicaid. Claims made in the period of 12 months prior to surgery (acute pain) or return of results (chronic pain, depression) through 6 months following those events will be collected. See Section 9 and the MOP for additional details. Schedule of Activities and Timeframe for Collection of Endpoints

Table 8. Data collection schedule

Data collection schedule, method of data collection, and timing

Outcome	Data source/instrument	Baseline	10 d ± 3 d	1 mo. ± 7 d	3 mo. ± 14 d	6 mo. ± 14 d
Pain Assessments						
Pain intensity	PROMIS Pain intensity scales	AP, CP	AP	AP, CP	AP, CP*	AP, CP
Pain intensity	PROMIS Numeric Rating Scale - Pain Intensity (NPRS)	AP	AP*	AP	AP	AP
Daily opioid dose & type of opioid use	Average daily mg morphine equivalents (MED) since discharge use of opioids: tramadol/ codeine vs others		AP*	AP		
Opioid use disorder	PROMIS - Prescription pain medication misuse subscale	AP, CP			AP, CP	AP, CP
Mobility	PROMIS mobility	AP	AP	AP	AP	AP
Depression Assessments						
Depressive state	PROMIS Emotional Distress - Depression 8b survey	CP, D		CP, D	CP, D*	CP, D
Depressive state	Patient Health Questionnaire-8 depression scale	D			D	D
Participant Medications						
Assessment of prescriptions	Custom survey/EHR	AP, CP, D	AP		CP, D	
Assessment of filled prescriptions	Medicaid and Medicare billing records for 12 months prior to time 0 through 6 months after time 0			AP, CP, D		

Adherence	Voils Medication Adherence		D		D	D	D
SSRI AE Survey	Custom survey		D		D	D	D
Opioid side effect survey	Adapted medication side effect survey (SPACE)		AP, CP	AP	AP, CP	AP, CP	AP, CP
Opioid persistence	Custom survey						AP
Participant Actions							
Interaction with provider	Participant visits				CP, D		
Interaction with test result	Custom survey						AP, CP, D
Quality of life and well being							
Past Medical History	Participant visits/custom survey		AP, CP, D				
Well-being	PROMIS43/PROMIS Peds37		AP, CP, D		AP, CP, D	AP, CP, D	AP, CP, D
Healthcare Utilization and Costs							
Medicare/Medicaid billing records	Medicaid and Medicare billing records for 12 months prior to time 0 through 6 months after time 0				AP, CP, D		
LoS	LoS for index admission			AP			

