ED/urgent care & inpatient visits	Participant reported visits				AP, CP, D	AP, CP, D	AP, CP, D
Outpatient visits	Participant reported primary care & pain clinic visits				AP, CP, D	AP, CP, D	AP, CP, D
Outpatient visits	Long-term care or in-patient rehab days, home healthcare days				AP	AP	AP
Productively Loss	Survey of lost work time and income				AP, CP, D	AP, CP, D	AP, CP, D

Abbreviations: CP – chronic pain, AP – acute post-surgical pain, D-depression, ED – emergency department, EHR – electronic health record; LoS – length of stay; PT – physical therapy

*Denote primary endpoints

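### Opioid usage, one of the two components of the acute-pain primary SIA score, has two conflicting time windows (past 7 days in Section 11.2, since discharge in Table 8); separately, Section 10.5 tests PHQ-8 response at 5% where the endpoint is 50%

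*Combined protocol and SAP*

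**What the plan says.** **Acute pain.** The primary endpoint is the SIA score at 10 days (Section 3.1). Section 11.2 builds it by ranking pain and opioid use, rescaling each set of ranks, and adding the two. Opioid usage at 10 days is also a secondary endpoint (Section 3.2).

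- Section 11.2 gives the window: "Opioid usage: The average daily morphine equivalents in mg (MED) in past 7 days". It names one source: "MEDs will be calculated using data from the opioid usage survey".
- Table 8 gives another: "Average daily mg morphine equivalents (MED) since discharge use of opioids". (The last words of that quote open a second item in the same cell, the type of opioid.) The 10-day acute-pain cell carries an asterisk, and the footnote says asterisks "Denote primary endpoints".
- Appendix A, which explains the score, gives no window.
- The opioid questionnaire in Section 7.3 covers the type of opioid plus "number of pills dispensed, if a refill has been obtained, and the number of pills left for each opioid pain medication selected". The list is introduced as non-exhaustive.

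Other data are planned that Section 11.2 does not cite. Section 7.3 says "Participant medications will be collected using patient surveys at baseline and the primary endpoint time points: 10-days for Acute Pain", and Table 8 has a row "Assessment of prescriptions" (survey or EHR, acute pain at baseline and day 10). Section 7.8 plans EHR prescription information, and Section 7.3 has a length-of-stay item at day 10. Section 10.2 promises a separate detailed SAP for each trial.

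**Depression.** The Synopsis and Section 3.2 define PHQ-8 response as a 50% reduction at 3 months. Section 10.5 says that a 5% reduction will be tested.

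**The concern.** An analyst who follows Section 11.2 and one who follows Table 8 would compute different opioid values for some participants. Those values would be ranked differently, and the ranks feed the primary endpoint. The component matters: Appendix A reports that the pilot found similar pain intensity in both arms but lower opioid consumption in the guided arm, so the pilot signal came from the opioid side of the score. SIA is also tested at the interim (Section 10.7), so one definition must hold at both looks. The trial is open label, and Section 10.9 relies on prespecified outcome variables in place of multiplicity adjustment. A variable with two definitions is not fully prespecified.

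The second question is whether the named source can deliver either window. The third, unrelated and smaller, is that a 5% PHQ-8 threshold would turn a response endpoint into almost any improvement.

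**Working it through.** **1. The plan's own figure.** Section 10.1 requires 152 actionable participants per arm (standardized effect 0.375, two-sided alpha 0.049, 90% power). Normal approximation: 2 × (1.9685 + 1.2816)² / 0.375² = 150.2, so 151. The two-sample t-test gives 151.2, so 152, with 90.1% power. The figure reproduces. It rests on an assumed standardized effect, so the choice of window does not change it.

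**2. The two windows side by side.** Let L = survey day minus discharge day. Table 8 allows 10 ± 3 days, so the survey day is 7 to 13.

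| L | Since discharge | Past 7 days, not cut | Past 7 days, cut at discharge |
|---|---|---|---|
| more than 7 | all L days | last 7 of them | last 7 of them |
| 7 | 7 days | same 7 days | same 7 days |
| fewer than 7 | L days | 7 days, of which 7 − L precede discharge | same L days |

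The windows always differ when L exceeds 7. Below 7 they differ only if the 7-day window is not cut at discharge, which Section 11.2 does not address. For assumed stays of 0 to 5 days, L runs from 5 to 10 at a day-10 survey, and from 2 to 13 over survey days 7 to 13.

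**3. What the listed survey items yield.** Pills dispensed minus pills left is a cumulative count since dispensing. As an illustration (not document figures), take 30 dispensed, 21 left and no refill, and assume dispensing on the day of discharge: N = 30 − 21 = 9 pills.

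- L = 10: since discharge 9/10 = 0.90 pills a day. The 7-day value is not determined; it lies between 0 (all taken in the first 3 days) and 9/7 = 1.29 (all taken in the last 7).
- L = 13: since discharge 9/13 = 0.69. The 7-day value lies between 0 and 1.29.
- L = 7: 1.29 on both.
- L = 4 (discharge day 3, survey day 7): since discharge 9/4 = 2.25. The 7-day value is 2.25 if cut at discharge, or 9/7 = 1.29 if not cut and only dispensed pills are counted.

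The listed items therefore do not isolate the last 7 days. They are not complete for the other window either. A refill is recorded as obtained or not, without a quantity, and tablet strength is not listed. If the dispensed count excludes a refill of r pills, use over L = 10 is (9 + r)/10, that is 1.9 to 3.9 a day for an assumed r of 10 to 30, against 0.90 without it.

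**4. Size on the SIA scale.** The figures in step 3 are pills per day for one invented participant and show nothing about ranks. A simulation gives some idea of scale. Its inputs are all assumed: 304 participants, stay 0 to 4 days, survey day 7 to 13, exponentially tapering use, pain independent of use, and a 7-day window not cut at discharge. Three taper settings were tried.

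| Taper constant | Spearman correlation, two opioid measures | Correlation, two SIA scores |
|---|---|---|
| 5 days for all | 0.91 | 0.96 |
| 3 to 10 days | 0.94 | 0.97 |
| 2 to 30 days | 0.98 | 0.99 |

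Part of the agreement in the last column is built in, because both SIA versions share the same pain ranks. With independent components of equal spread the correlation is about (1 + r)/2; for example (1 + 0.91)/2 = 0.96.

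**5. PHQ-8.** Scores are integers from 0 to 24 (Section 11.2). Points needed from baseline b are 0.05b or 0.5b, rounded up.

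| Baseline | 5% | 50% |
|---|---|---|
| 10 | 1 | 5 |
| 15 | 1 | 8 |
| 20 | 1 | 10 |
| 24 | 2 | 12 |

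At 5%, a one-point drop is a response at any baseline from 1 to 20.

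**The case against.** The separate SAP and the MOP, neither of which is among these documents, may already fix the window, and a short data-element definition need not list every input. The questionnaire list is open-ended, so a 7-day item may exist. Prescription data and length of stay are collected. SIA uses ranks, and the simulated effect is small. The 5% is probably a dropped zero.

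Much of this stands. The missing source detail is partly a matter of where the plan chooses to put it. The conflict itself remains: whichever window the SAP adopts, either Section 11.2 or Table 8 is then wrong and needs correcting.

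Stronger readings are tempting, but the documents do not support them:

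- A reader might infer that the needed data are not collected. Sections 7.3 and 7.8 plan data that could supply quantity, strength and discharge date; Section 11.2 simply does not point to them.
- A reader might prefer 7 days because the PROMIS pain scale asks for "average pain over the last 7 days, worst pain over the last 7 days, and current pain". Table 8 instead stars the Numeric Rating Scale as the day-10 acute-pain measure, and Section 7.3 gives that scale no recall period.
- A reader might say the windows agree only when discharge is exactly 7 days before the survey. If the 7-day window is cut at discharge, they agree for every shorter interval too.

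**Conclusion.** The contradiction is in current text, concerns a component of the acute-pain primary endpoint, and is not settled elsewhere in the documents. It should be corrected before analysis. That the windows differ follows from the day counts alone. That the listed items cannot give a 7-day value holds unless the survey contains an item not listed in Section 7.3.

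The effect on SIA is not known from the documents and may be modest; the correlations of 0.96 to 0.99 rest entirely on assumed inputs. A reader might infer that the primary test is biased or underpowered, or that the sample size is wrong. None of these is shown: no difference between arms in how the window acts has been established, and the stated 152 per arm reproduces.

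The PHQ-8 discrepancy is certain but minor. It affects one secondary endpoint of the depression trial, and two sections agree on 50%.

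**What to change.** **Acute pain.** Before any unblinded analysis, including the interim, state one window in both Section 11.2 and Table 8. Give its denominator in days, and name the sources of tablet strength and refill quantity.

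- Use since discharge by default. It can be built from the opioid survey, the length-of-stay item and EHR prescription data, assuming dispensing at or near discharge.
- If the survey does hold a 7-day consumption item, the past 7 days may be kept. Then correct Table 8 and say whether the window is cut at discharge.

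The cost is wording, plus confirming that the EHR extract carries quantity and strength and that the survey completion date is recorded. If 7 days is wanted and no such item exists, participants already surveyed cannot supply it afterwards, so the questionnaire should be checked first. No sample size changes.

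**Depression.** In Section 10.5, change 5% to 50%. This costs one word.

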3.2 Secondary Endpoints

Secondary endpoints include:

All Trials

1. Overall well-being at 6-month follow-up
2. Sub-domains of overall well-being: pain interference, physical function, sleep disturbance, social role and activities functioning, fatigue, anxiety, and depression at 6-month follow-up
3. Concordance between metabolizer phenotype and prescribed medication

Acute pain

1. Pain intensity at 10 days post-surgery
2. Opioid usage at 10 days post-surgery
3. Prescription pain medication misuse score at 3-months post-surgery
4. Mobility at 1-month post-surgery
5. Opioid persistence 6 months post-surgery

Chronic pain

1. Pain reduction magnitude at 3-month post return of genetic testing results to provider, relative to baseline
2. Proportion of participants achieving clinically significant pain reduction (30% reduction from baseline) at 3-months post return of genetic testing results to provider
3. Prescription pain medication misuse at 3-months post return of genetic testing results to provider

Depression

1. Change in PHQ-8 score between baseline and 3 months
2. Achieve 50% reduction in PHQ-8 scores at 3 months, relative to baseline
3. Medication side effects severity burden at 3 months
4. Participant medication adherence at 3 months
5. Achieve remission at 6 months, defined as PROMIS depression score ≤ 16
6. Achieve remission at 6 months, defined as PHQ-8 score ≤ 4

4. Study Arms & Design

This is a prospective, multicenter, subset analysis of 1:1 randomized Intervention (immediate PGx testing and genotype-guided opioid or SSRI therapy with clinical decision support) vs. Control (usual care with delayed PGx testing) pragmatic, open label clinical trial (Figure 1). The three trials are 1) genotype-guided opioid therapy among post-surgical acute pain participants (Acute Pain, Figure 1A), 2) genotype-guided opioid therapy among chronic pain participants (Chronic Pain, Figure 1B), and 3) genotype-guided SSRI therapy in participants with depression (Depression, Figure 1C). Trial-specific outcomes will be compared between participants in the intervention arm and control arms who have an actionable phenotype. Actionable phenotypes are defined as CYP2D6 IM and PMs (i.e. CYP2D6 activity score ≤ 0.75) for the acute pain and chronic pain trials and CYP2C19 UM, RM and PMs or CYP2D6 UM and PMs for the depression trial.

[figure not shown]

Figure 1. ADOPT PGx Trial Design

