7.3 Follow-up Participant Assessments

The event that starts the post-intervention data collection timing are as follows.

Acute Pain:

- Date of surgery (intervention and control arms)

Chronic Pain and Depression:

- Intervention arm: When the pharmacogenetics results are returned to the provider and deposited in the EMR
- Control arm: At date of DNA sample collection plus one week, where one week reflects the average time from sample collection to returning the results to the EHR
- Note: There will be variability in time the results are returned to provider and when genotype-guided therapy is delivered to the participant, time from results being available to the next provider-participant interaction (e.g. email, clinic visit, new prescription order, phone visit, etc.) will be recorded by study personnel.

Post intervention assessment collection may be done by the University of Florida College of PharmacyCall Center. The center agents will be trained survey collectors*, using an IRB approved telephone script. The collected survey responses will be entered into the study database. If preferred, the participant will have the option to complete the study follow-up survey by a URL link sent by text (to mobile phone) or email and captured in REDCap database

In the event that the call center is unable to reach a participant, local study coordinators may contact participants to facilitate completion of the follow-up surveys.

Data will be collected in the following timeframes*:

- Acute pain: 10 days, 1 month, 3 months, and 6 months post-surgery
- Chronic pain and depression: 1-month, 3 months, and 6 months post return of results for the intervention arm, and post baseline assessments for the control arm.

*See *MOP for call center agents and survey collection interval windows*

All Trials

PROMIS 43 – Adults (≥ 18 years of age) will complete a 43-question survey assessing well-being and sub domains: pain interference, physical function, sleep disturbance, social role and activities functioning, fatigue, anxiety, and depression.[32] This survey will be administered to adult participants at baseline, 1-month, 3-months, and 6-months post-surgery (acute pain), or baseline, 1-month, 3-months, and 6-months post return of results (chronic pain, depression).

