10.5 Analysis of the Secondary Endpoints

All Trials

To determine the effect of genotype-guided drug therapy on overall well-being and the well-being sub-domains (pain interference, physical function, sleep disturbance, social role and activities functioning, fatigue, anxiety, and depression) in acute pain, chronic pain, and depression participants, we will conduct an intent to treat analysis, comparing the well-being (or sub-domain) T-scores from the 6-month follow-up assessments in the Intervention group compared to the control group using a two-sided two-sample t-test or Mann Whitney test, as appropriate, stratified by participant population (acute pain, chronic pain, depression), with a type 1 error of 0.05.

Acute Pain

The effect of genotype-guided opioid therapy on secondary endpoints pain intensity, opioid usage, opioid misuse score, and mobility score will be assessed by comparing the Intervention group subset with CYP2D6 IM or PM phenotypes to the Control group subset with CYP2D6 IM or PM phenotypes using a two-sided two-sample t-test or Mann Whitney test, as appropriate, with a type 1 error of 0.05. The effect of genotype guided opioid therapy on the secondary endpoint opioid persistence will be assessed by comparing the Intervention group subset with CYP2D6 IM or PM phenotypes the Control group subset with CYP2D6 IM or PM phenotypes using a test of two-proportions with an alpha of 0.05. Participants with other CYP2D6 phenotypes will not be included in these analyses.

Chronic Pain

The effect of genotype-guided opioid therapy on secondary endpoints pain intensity reduction and opioid misuse score will be assessed by comparing the Intervention group subset with CYP2D6 IM or PM phenotypes to the Control group subset with CYP2D6 IM or PM phenotypes using a two-sided two-sample t-test or Mann Whitney test, as appropriate, with a type 1 error of 0.05. The effect of genotype guided opioid therapy on the secondary endpoint clinically significant pain reduction, defined as a 30% decrease, will be assessed by comparing the Intervention group subset with CYP2D6 IM or PM phenotypes the Control group subset with CYP2D6 IM or PM phenotypes using a test of two-proportions with an alpha of 0.05. Participants that have other CYP2D6 phenotypes will not be included in these analyses.

Depression

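### Section 11.2 builds overall well-being from the summed responses to the whole PROMIS 43/37, mixing ability and deficit domains with no alignment step and no stated direction of benefit

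*Combined protocol and SAP*

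**What the plan says.** Section 3.2 puts "Overall well-being at 6-month follow-up" first among the secondary endpoints for all trials, and the synopsis lists the effect on overall well-being among its all-trials objectives.

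Section 11.2 gives the scoring rule: "Defined as the T-score converted summed responses to the PROMIS 43/PROMIS 37 pediatrics survey". It adds only the scale: "The T-score conversion is centered around 50 with standard deviation of 10".

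Section 7.3 shows what is summed. Adults "will complete a 43-question survey assessing well-being and sub domains: pain interference, physical function, sleep disturbance, social role and activities functioning, fatigue, anxiety, and depression". Participants aged 8 to 17 "will complete a 37-question survey assessing pediatric well-being and sub domains: pain interference", followed by the same remaining domains.

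Section 10.5 analyses the endpoint by intent to treat, "comparing the well-being (or sub-domain) T-scores from the 6-month follow-up assessments in the Intervention group compared to the control group", with a two-sided test at 0.05 within each trial population. The seven sub-domains are a separate secondary endpoint in section 3.2: "Sub-domains of overall well-being: pain interference, physical function, sleep disturbance, social role and activities functioning, fatigue, anxiety, and depression at 6-month follow-up".

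**The concern.** Two of the seven domains are named as abilities: physical function, and social role and activities functioning. The other five are named as deficits: pain interference, sleep disturbance, fatigue, anxiety and depression. A participant who gets better would normally go up on the first group and down on the second. Summing responses across both groups without reversing one of them sets these movements against each other.

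A mean of 50 and a standard deviation of 10 fix a scale but not an orientation. Section 11.2 is more careful with the SIA score, where it says how the parts are combined and what negative and positive values mean.

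The test is two-sided, so a significant difference in overall well-being could not be read as benefit or harm from the protocol alone. Section 10.9 makes no multiplicity adjustment and relies instead on consistency across prespecified endpoints. A score with no stated direction cannot be checked for consistency. Choosing its orientation after the data are seen, in an open-label trial, would undo the prespecification.

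**Working it through.** **Plan's own figure.** None. The documents give no effect size, power or expected value for overall well-being, so what follows is an illustration.

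**Inputs from the documents.** Seven domains, two ability and five deficit (7.3); one sum over the whole survey (11.2); two-sided 0.05 (10.5); completers per arm of 447 (chronic pain), 678 (depression) and 845 (acute pain) (10.1).

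**Assumptions, not in the documents.**
- Each domain is coded in the direction of its name, with no reversal.
- The domains have equal weight and equal variance.
- Once aligned so that higher is better, all pairs of domains share one correlation ρ, varied from 0 to 0.7.
- Where a size is needed, improvement is d = 0.1 SD per domain.

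**Step 1: lean of the sum.** Assume also six items per domain scored 1 to 5, ignoring the one remaining adult item. Best health gives 30×1 + 12×5 = 90, mid-scale answers give 42×3 = 126, and worst health gives 30×5 + 12×1 = 162. The sum leans towards higher meaning worse. Its healthy-to-ill span is 162 − 90 = 72 points, out of 42×4 = 168 possible.

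**Step 2: uniform benefit, raw change.** Five domains fall and two rise, so the net is (5 − 2)/7 = 43% of the aligned change.

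**Step 3: uniform benefit, standardised.** With weights w, the effect is Σ(w·d) / √(7 + ρ((Σw)² − 7)).
- Aligned (Σw = 7): 7d / √(7 + 42ρ).
- Unreversed (|Σw| = 3): 3d / √(7 + 2ρ), in absolute value.

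| ρ | Aligned | Unreversed | Share kept |
|---|---|---|---|
| 0 | 0.265 | 0.113 | 43% |
| 0.3 | 0.158 | 0.109 | 69% |
| 0.5 | 0.132 | 0.106 | 80% |
| 0.7 | 0.116 | 0.104 | 89% |

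**Step 4: power at ρ = 0.5, aligned to unreversed.** 51% to 35% with 447 per arm, 68% to 50% with 678, and 78% to 59% with 845.

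**Step 5: selective benefits.**
- Equal gains in pain interference and physical function only: −d + d = 0. A real benefit on both leaves the score unchanged.
- Gains in the two function domains only: +2d / √(7 + 2ρ), which is +0.071 at ρ = 0.5.
- Gains in the five symptom domains only: −5d / √(7 + 2ρ), which is −0.177 at ρ = 0.5.

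The last two are both improvements, yet they have opposite signs. So the sum is not monotone in well-being.

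**The case against.** **The coding is not in the documents.** This is the strongest point, and it stands. No section gives the item coding of the PROMIS 43 or pediatric 37. The closest evidence is indirect. In 11.2 a low depression 8b sum means remission, and in 7.3 higher pain intensity values mean more pain; both fit the assumption for symptoms. For function, 7.3 gives only the response order of the separate mobility survey, from able to unable, without numbers. If the function items were coded so that higher is worse, the sum would already be aligned. The cancellation would disappear, and only the missing statement of direction would remain.

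**A reader might infer that improvements cancel, or that the score has no direction.** The documents do not support either reading. With five symptom domains against two function domains, a uniform benefit is diluted, not cancelled, and the score leans towards higher meaning worse. Exact cancellation needs a balanced pattern. For a benefit confined to symptoms, the unreversed sum is even the more sensitive of the two: 0.177 against 5d/√28 = 0.094 at ρ = 0.5.

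**A reader might infer that the well-being objective has no other endpoint.** It has: 3.2 and 10.5 test all seven sub-domains, so a composite at odds with its parts would be visible. That limits the harm. It does not make the composite interpretable.

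**Scoring may be settled elsewhere.** Section 10.2 announces a separate statistical analysis plan for each trial, and 7.3 points to the published PROMIS surveys. Either could supply the missing steps. But 11.2 is not silent: it states a positive rule, the sum of the responses, and any other scoring would depart from that text.

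**Conclusion.** Wrong as written, conditional on each domain being coded in the direction of its name. The stated rule combines ability and deficit domains without aligning them, and the protocol does not say which end of the score is better.

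Under that coding, with equal weights and variances, a uniform benefit keeps 43% of the raw change and about 43% to 89% of the standardised effect for ρ from 0 to 0.7. Balanced gains can net to zero, and function-only gains look like the reverse of symptom relief. The power figures further assume 0.1 SD per domain and ρ = 0.5; the documents supply neither value.

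The missing direction of benefit does not depend on the coding assumption. No primary endpoint is affected, and the separate sub-domain tests contain the damage. Even so, this is the first-listed secondary endpoint shared by all three trials, and it should be corrected before analysis.

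**What to change.** In 11.2, replace the summed-response rule for overall well-being:

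1. Score each of the seven domains to its own T-score, and state the orientation of each.
2. Reverse the five symptom domains as 100 − T.
3. Average the seven, so that higher is better.
4. Either rescale the average to mean 50 and SD 10, or drop that statement for the composite. An average of seven T-scores has SD 10·√((1 + 6ρ)/7), which is 3.8 at ρ = 0, 7.6 at ρ = 0.5 and 8.6 at ρ = 0.7. It equals 10 only if the domains are perfectly correlated.
5. Apply the same rule to the pediatric form, for which 7.3 lists the same seven domains.

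State the direction of benefit in 3.2 and 10.5, and carry the definition into each trial's statistical analysis plan. The sub-domain analyses stay as they are.

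The cost is one definition and two short cross-references, with no new data and no added participant burden.
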